# 5. STUDY CONDUCT

# 5.1 **Restrictions during the study**

Restrictions regarding laxative use, change in opioid dose, and restricted medications are provided in Section 5.6.

# 5.2 Subject enrollment and randomization

Patients will keep the same randomization number and the same enrollment number that they had in study D3820C00004.

The Principal Investigator (PI) or other qualified designee will:

- 1. Obtain signed informed consent from the potential patient before any study-specific procedures are performed.
- 2. Determine patient eligibility. Eligibility will be determined at Visit 1.

If a patient discontinues from participation in the study, then his/her enrollment/randomization code cannot be reused.

# 5.3 **Procedures for handling subjects incorrectly enrolled**

Patients who fail to meet the I/E criteria should not, under any circumstances, be enrolled. There can be no exceptions to this rule.

In cases where patients who do not meet the selection criteria are incorrectly started on treatment, or where patients subsequently fail to meet the study criteria post initiation, a discussion should occur between the Study Physician and the investigator regarding whether to continue or discontinue the patients from treatment. The Study Physician is to ensure all such decisions are appropriately documented.

# 5.4 Blinding and procedures for unblinding the study

# 5.4.1 Methods for ensuring blinding

NKTR-118 12.5 and 25 mg tablets will be identical in size and color to their respective placebo tablets. Packaging and labeling of the investigational products (IPs) will be performed in a way to ensure blinding throughout the study. Patients will receive 2 tablets per dose, irrespective of which randomized dose they receive.

No member of the study team in AstraZeneca or its representative, at investigational centers or any contract research organization (CRO) handling data will have access to the randomization scheme during the conduct of the study with the exception of AstraZeneca's Research and Development Supply Chain and Patient Safety. The blinding should remain intact for this study even after unblinding of study D3820C00004.

The randomization schedule for blinding of randomized treatment will be maintained by AstraZeneca and will not be disclosed until after database lock.

# 5.4.2 Methods for unblinding the study

If a treatment code break is required, this will be done via the interactive voice response system (IVRS). Individual treatment codes, indicating the assigned treatment for each randomized patient, will be available to the investigator(s) or pharmacists from the IVRS. Routines for this will be described in the IVRS user manual that will be provided to each center.

The treatment code should not be broken except in medical emergencies when the appropriate management of the patient requires knowledge of the treatment randomization. If the treatment code is broken, then the investigator must document and report the action to AstraZeneca or its representative, without revealing the treatment given to the patient to AstraZeneca staff or its representative.

AstraZeneca retains the right to break the code for SAEs that are unexpected and are suspected to be causally related to an IP and that potentially require expedited reporting to regulatory authorities. Treatment codes will not be broken for the planned analyses of data until all decisions on the evaluability of the data from each individual patient have been made and documented.

### 5.5 Treatments

#### 5.5.1 Identity of investigational product(s)

Study drug tablets will be round, biconvex, and white film coated. Tablets will be supplied in high-density polyethylene (HDPE) bottles, dispensed every 30 days. Each 30-day supply will consist of 2 bottles of study drug, each containing 35 tablets.

AstraZeneca will provide the study treatment as follows in Table 2:

Table 2 Study drug				
Investigational product	Dosage form and strength	Manufacturer		
NKTR-118	Tablet, 12.5 mg	Pharmaceuticals International, Inc.		
NKTR-118	Tablet, 25 mg	Pharmaceuticals International, Inc.		
Matching placebo to NKTR-118 12.5 mg	0 mg	Pharmaceuticals International, Inc.		
Matching placebo to NKTR-118 25 mg	0 mg	Pharmaceuticals International, Inc.		

#### Table 2Study drug

### 5.5.2 Doses and treatment regimens

Patients will receive study drug during the 12-week treatment period of the study (Days 2 to 85). Patients will be instructed to take 1 tablet from each bottle 1 hour before eating in the morning.

NKTR-118 or placebo will be administered once daily, as 2 tablets. Patients will receive NKTR-118 12.5 mg, or 25 mg, or placebo, as specified in Table 3.

NKTR-118					
Treatment day	12.5 mg/day	25 mg/day	Placebo		
Days 2 to 85	1 x 12.5 mg NKTR-118 tablets	1 x 12.5 mg placebo tablets	1 x 12.5 mg placebo tablets 1 x 25 mg		
	1 x 25 mg placebo tablets	1 x 25 mg NKTR-118 tablets	placebo tablets		

Table 3Administration of investigational product

### 5.5.3 Additional study drug

Sites will procure bisacodyl 5 mg tablets for use as laxative rescue medication and will dispense bisacodyl to patients at Visits 1, 2, and 3.

Information regarding rescue laxative and opioid medication for breakthrough pain is provided in Section 5.6.

### 5.5.4 Labeling

All clinical trial material will be packaged and labeled by AstraZeneca. The clinical trial material will be clearly marked according to national requirements regarding use for clinical trial investigation only and will also be labeled with the drug name, study reference number, and storage conditions. It is the responsibility of the investigator to ensure that accurate accountability records are maintained throughout the study.

AstraZeneca will provide the IP to the study sites. Labels will be prepared in accordance with Good Manufacturing Practice (GMP) and local regulatory guidelines. The labels will fulfill GMP Annex 13 requirements for labeling. Label text will be translated into local language.

#### 5.5.5 Scheduling classification

The control or classification of NKTR-118 as a controlled substance is country dependent. NKTR-118 is currently not controlled in either the UK or in Sweden. The US Drug Enforcement Administration (DEA) has classified NKTR-118 as a Schedule II (C-II) substance based on structural relatedness to noroxymorphone. Preclinical studies of NKTR-118 demonstrated that NKTR-118 has u-opioid antagonistic properties, and abuse liability studies are currently underway to further determine control classification. Additional details regarding safety surveillance activities for NKTR-118 are provided in the Safety Handling Plan.

#### 5.5.6 Storage

All IPs must be kept in a secure place under appropriate storage conditions. A description of the appropriate storage and shipment conditions is specified on the IP label and in the IB. All study drug will be stored in original containers until dispensed to the study patients.

The receipt, handling, storage and dispensing of NKTR-118 will be in accordance with applicable country regulatory requirements.

# 5.6 **Concomitant and post-study treatment(s)**

Throughout the study, investigators will be encouraged to maintain a patient's baseline pain control regimen, with dose adjustments made as needed in accordance with the patient's clinical needs. Investigators will retain latitude in making these adjustments as clinically indicated, but it is recommended that the guidelines for the ongoing management of pain in the study reference manual (Chou et al 2009) serve as a framework for dose adjustments on-study. It is anticipated that the majority of the patients in this study will be receiving a long-acting opioid for control of background pain and an immediate-release opioid as needed (PRN) for breakthrough pain, although some may be receiving only a short-acting opioid on a scheduled basis.

It is recognized that some patients may have their pain managed by personal physicians who are not connected with the study. In these cases, patients will be asked to notify their personal physicians of their participation in the study, and to ask their physicians to notify the study investigator should a change in their pain control regimen be made.

Concomitant non-opioid analgesics will not be prohibited, but investigators will be encouraged to maintain such drugs at stable doses on-study if possible.

During the treatment period, a patient may take bisacodyl as a laxative rescue medication only if a BM has not occurred within at least 72 hours. If after a minimum of 72 hours, the patient has not experienced a BM, he/she may take bisacodyl rescue therapy (10 to 15 mg dose, ie, 2 to 3 bisacodyl tablets at a time). If the patient remains constipated, bisacodyl rescue therapy may be repeated up to 2 additional times, as necessary, each 10 to 15 mg dose separated by 12 hour intervals. It is recommended that the bisacodyl tablets be taken either at bedtime or before breakfast. If after 3 doses of bisacodyl rescue therapy, the patient still has not experienced a BM, the investigator may prescribe one-time use of an enema. The timing of administration of this therapy should be noted in the home diary. In addition, the site is to record any enema prescription on the enema eCRF. If these secondary interventions fail, the patient should be discontinued from the study and referred for additional medical evaluation. Since the patient is discontinued from the study, the investigator should recommend initiation of any therapy deemed most appropriate. Any patient who is obstipated and/or has fecal impaction must not be enrolled (see Section 4.2).

During the study, it is advised that the PI be responsible for managing the patient's constipation. Study centers will procure and dispense bisacodyl for use as rescue medication, which will be dispensed to patients at each visit, starting with Visit 1. Patients will be instructed on the guidelines for rescue bisacodyl use. Patients will be asked to return unused bisacodyl at each subsequent visit. Bisacodyl use will be determined at each visit by counting the number of unused bisacodyl tablets returned.

Unless there is a need for urgent intervention, patients will not be allowed to take any additional medication for pain control or treatment of constipation, other than their maintenance opioid regimen and approved opioid medication for breakthrough pain, and bisacodyl, during the course of the study without the prior agreement of the investigator (or their personal physician, if pain is managed outside the study, in which case the investigator must be notified of any changes). This includes over-the-counter treatments for constipation and pain.

Changes in the opioid regimen may be made to ensure appropriate pain control. Any changes must be recorded in the daily maintenance opioid dosing regimen and/or breakthrough pain medication eCRFs, as appropriate.

The following laxative medications are prohibited on-study; however, they do not constitute an exhaustive list:

- Milk of magnesia or magnesium citrate
- Non-absorbable phosphate
- Cascara

Revised Clinical Study Protocol Drug Substance NKTR-118 Study Code D3820C00007 Edition Number 2.0 Date

- Senna
- Castor oil/mineral oil
- Epsom salt
- Lactulose
- Polyethylene glycol
- Docusate
- Enemas
- Tegaserod
- Lubiprostone (Amitiza®)
- Drugs blocking fat absorption with an associated laxative effect
- Prucalopride
- Prune juice
- Herbal preparations for constipation
- Bulk laxatives, such as psyllium and methylcellulose.
- Any agent that is used in an off-label fashion to treat constipation (eg, colchicine, misoprostol, erythromycin, cholinesterase inhibitors such as donezepil)
- Any experimental constipation therapy

The following opioid antagonists and mixed agonists/antagonists are also prohibited:

- Pentazocine
- Buprenorphine
- Nalbuphine
- Naloxone and other naloxone containing products, such as oxycodone/naloxone combinations (eg, Targin®)
- Naltrexone and other natrexone containing products such as morphine/naltrexone combinations (eg, Embeda®)

- Methylnaltrexone (Relistor®)
- Alvimopan (Entereg®)

The following strong inhibitors of cytochrome P450 3A4 (CYP3A4) and P-glycoprotein (PGP) are prohibited:

- Cyclosporine
- Indinavir
- Nelfinavir
- Ritonavir
- Ketoconazole (except for topical use)
- Itraconazole
- Verapamil

Other medication, which is considered necessary for the patient's safety and well-being, may be given at the discretion of the investigator and recorded in the appropriate sections of the eCRF.

# 5.7 Treatment compliance

Each patient is expected to comply with the treatment regimen during the study. The administration of the study drug should be recorded in the appropriate section of the eCRF. Compliance with the study drug will be assessed by comparing the number of tablets dispensed minus the number of tablets returned versus the number of tablets that should have been taken (2 tablets per day).

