## 13.2 Overdose

For the NKTR-118 program, overdose is defined as a dose ingested (or taken via any other route), confirmed by the patient (if possible), in excess of the total daily dose specified for the patient in their treatment group of the protocol. All reports of overdose (with or without associated AEs) are to be collected.

No cases of overdose have been previously reported with NKTR-118. No specific antidote for overdose with NKTR-118 has been identified to date.

If a patient on opioid therapy receives an overdose with NKTR-118, the patient should be monitored closely for evidence of opioid withdrawal symptoms and reversal of central analgesic effect. In cases of known or suspected overdose, symptomatic treatment as well as monitoring of vital functions should be performed. In cases of severe intoxication, intensive care procedures are recommended. Close medical supervision and monitoring should be continued until the patient recovers.

For recording purposes:

- If an overdose is reported during the course of a study, the patient is evaluated by the investigator/site staff to determine whether an SAE, non-serious AE, or no symptoms have been experienced after the overdose has been taken.
- If the patient experiences an overdose with an associated SAE, the investigator/site staff will capture details of the SAE and associated information on OVERDOSE, AELOG, and SAE modules in the eCRF.
- If the patient experiences an overdose with an associated non-serious AE, the investigator/site staff will capture details of the non-serious AE and associated information on OVERDOSE and AELOG modules in the eCRF.
- If the patient experiences an overdose with no symptoms, the investigator/site staff will capture details of the overdose and associated information on OVERDOSE module only in the eCRF.
- The OVERDOSE module (found in Module Package Library) is the preferred way of collecting overdose information. If the OVERDOSE module cannot be used, for example, if a CRO is managing the study and is unable to use the module, the Clinical Study Overdose template, may be used. This form is also used if the overdose occurred in a person not enrolled in the study, eg, accidental ingestion by a relative of the patient.

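### Section 5.7 pools tablets from two bottles although only one is active in each NKTR-118 arm, so 100% compliance over 28 days fits 75% to 125% of the planned active tablets

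*Protocol*

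**What the plan says.** Section 5.7 defines compliance as one ratio over all study tablets: the "number of tablets dispensed minus the number of tablets returned versus the number of tablets that should have been taken (2 tablets per day".

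The supply and regimen have two parts. Section 5.5.1: "Each 30-day supply will consist of 2 bottles of study drug, each containing 35 tablets". Section 5.5.2: "Patients will be instructed to take 1 tablet from each bottle 1 hour before eating in the morning". Section 5.4.1 adds: "Patients will receive 2 tablets per dose, irrespective of which randomized dose they receive".

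Table 3 (Section 5.5.2) gives the daily content. The 12.5 mg arm takes "1 x 12.5 mg NKTR-118 tablets" with "1 x 25 mg placebo tablets". The 25 mg arm takes "1 x 25 mg NKTR-118 tablets" with a placebo matching the 12.5 mg tablet. In the placebo arm both tablets are placebo.

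The procedures for Visits 2, 3 and 4 (Sections 3.1.2 to 3.1.2.2) call for the number of unused tablets. Section 5.7.1.1 calls for the amount returned. Neither mentions a count by bottle.

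Two other sections bear on the same behaviour. Section 13.2 defines overdose as intake "in excess of the total daily dose specified for the patient in their treatment group of the protocol". Section 5.8 lists severe non-compliance, including with the dosing regimen, as a ground for discontinuation.

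**The concern.** In a double-dummy regimen the two tablets are not interchangeable. A patient who takes two tablets from one bottle and none from the other has the right total for the day, but has taken either no active drug or twice the assigned amount. The Section 5.7 ratio scores that day as fully compliant.

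The primary objective is to describe safety and tolerability at 12.5 mg and 25 mg against placebo, so a reader will take the compliance figure as evidence that patients took the assigned dose. Little else in the protocol would correct that impression. Pharmacokinetics is marked not applicable (Section 6.6), and the home diary is described for breakthrough opioids, other concomitant medication and enema timing, not for study drug. What is at stake is whether the compliance measure can signal net misuse of the active bottle, including possible intake above the assigned daily dose.

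**Working it through.** **Inputs**
- Bottle size: 35 tablets, two bottles per supply (Section 5.5.1).
- Regimen: 1 tablet per bottle per day (Section 5.5.2).
- Dosing: Days 2 to 85, which is 84 days. Study drug is dispensed at Visits 1, 2 and 3, so 84/3 = 28 days per interval on schedule.
- Visit window: ±3 days (Table 1).
- Assumptions: one supply per interval, and every tablet not returned was taken.

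**The plan's own denominator.** 1 + 1 = 2 tablets per day, or 2 × 28 = 56 per interval and 2 × 84 = 168 over the study. This reproduces the figure in Section 5.7.

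**What a pooled 100% allows.** Let A and P be the tablets used from the active and placebo bottles over D days. Pooled compliance = (A + P)/(2D). At 100%, A + P = 2D. Neither bottle can supply more than 35, so A lies between 2D − 35 (or 0 if that is negative) and 35. Active compliance is A/D.

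| Days D | Expected 2D | Active tablets at pooled 100% | Active compliance |
|---|---|---|---|
| 22 | 44 | 9 to 35 | 41% to 159% |
| 25 | 50 | 15 to 35 | 60% to 140% |
| 28 | 56 | 21 to 35 | 75% to 125% |
| 31 | 62 | 27 to 35 | 87% to 113% |
| 34 | 68 | 33 to 35 | 97% to 103% |

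D = 25 and 31 arise when one visit moves by 3 days. D = 22 and 34 arise when two adjacent visits move in opposite directions.

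In milligrams over 28 days:
- 12.5 mg arm: 21 × 12.5 = 262.5 to 35 × 12.5 = 437.5, against 28 × 12.5 = 350 planned.
- 25 mg arm: 21 × 25 = 525 to 35 × 25 = 875, against 28 × 25 = 700 planned.

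**One pattern that reaches the bound.** The patient empties the active bottle first at two tablets a day. That gives 17 days with two active tablets, 1 day with one, and 10 days with none: 17 × 2 + 1 = 35 active and 1 + 10 × 2 = 21 placebo. Pooled compliance is (35 + 21)/56 = 100%.

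**Early stop.** Over 17 dosing days, 34 tablets can all come from one 35-tablet bottle. Pooled compliance is 34/34 = 100%. Active compliance is 34/17 = 200% or 0/17 = 0%.

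**The same data counted by bottle.** In the 28-day pattern the bottles read 35/28 = 125% and 21/28 = 75%, so the imbalance shows. In the early-stop case they read 200% and 0%.

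**Limit of bottle counts.** If the patient takes two tablets from one bottle on 14 days and two from the other on the remaining 14, each bottle reads 28/28 = 100%. Day-level swaps that cancel out are invisible to any end-of-interval count.

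**The case against.** The strongest reply is that nothing planned depends on this ratio. The safety set needs one dose, and the efficacy set one dose and one assessment (Sections 12.1.1 and 12.1.2). The protocol states no compliance threshold or per-protocol set. Total exposure (Section 12.2.1) is not said to come from pill counts, and the one explicit exposure denominator is days on study drug (Section 11.6.2). This stands. A reader might infer that the pooled count misstates exposure or blurs the two dose groups. The documents do not support that: a dosing error would do so however compliance is computed, and no exposure calculation is linked to the ratio.

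A reader might also infer that overdoses would go unreported. Section 13.2 relies on reports and, where possible, the patient's confirmation. Section 5.8 relies on the investigator's judgement in consultation with the study physician. Neither uses the compliance ratio as its detector, and staff who receive both bottles can see that one is empty. What remains is narrower: the ratio adds no signal to those routes.

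It would likewise go too far to set stray doubled days in the 25 mg arm beside the Phase II discontinuations at 50 mg. Those arose under assigned daily dosing.

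Finally, the eCRF is not shown and may already hold counts by bottle, and site accountability records might too. That is possible and affects the cost of the fix. It does not repair Section 5.7, whose formula would discard the information.

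**Conclusion.** The point holds as a weakness of the compliance measure. At a pooled 100% over 28 days, active intake can be anywhere from 75% to 125% of plan. For a patient stopping by about 17 dosing days it can be 0% or 200%. The 35-tablet bottle caps the error: neither omission nor doubling can run through a full 28-day interval at pooled 100%.

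These are bounds under the assumptions above, not expected values. Reaching them over 28 days requires one bottle to be emptied. The protocol gives no information on how often patients would confuse the bottles, and the placebo arm is unaffected. The consequence is that the ratio cannot show net under-use or over-use of the active bottle. It also gives no signal of possible intake above the assigned daily dose (Section 13.2) or of this form of non-compliance (Section 5.8). Importance is modest, but the change is worth making because it is specific and nearly free.

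**What to change.** In Section 5.7, the visit procedures and Section 5.7.1.1:

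- Record returned tablets separately by blinded bottle identifier at Visits 2, 3 and 4/early termination.
- Compute compliance per bottle as (dispensed − returned)/(1 × dosing days).
- After unblinding, report active-bottle compliance by arm.
- Raise a data query when a bottle has more tablets missing than dosing days, with lost tablets to be ruled out first.
- State that end-of-interval counts detect only net imbalance between bottles, not swaps that cancel out.

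The cost is one extra count per visit, if the eCRF does not already hold it, and a changed derivation. The bottles are already separate and already returned, so no visit or procedure is added. With blinded identifiers the blind is kept. The change concerns measurement only and alters no dose or clinical rule.

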#### 5.7.1 Accountability

### 5.7.1.1 NKTR-118

The study drug provided for this study will be used only as directed in the CSP.

The study personnel will account for all study drugs dispensed to and returned from the patient. This record-keeping consists of a dispensing record that includes the identification of the person to whom the study drug is dispensed, the quantity and the date of dispensing, and the amount of any unused study drug returned to the investigator. This record is in addition to any drug accountability information recorded on the eCRF. Patients must return unused study drug supplies to the investigator at each visit in which new study drug is dispensed, and at the final visit of the treatment period.

Study site personnel will account for all received study drugs and return all unused study drugs to AstraZeneca or its representative for study drug destruction in accordance with applicable country regulatory requirements. Certificates of delivery and return should be signed.

